## 2.4 Pediatric Studies

There is no prior experience with IMGN901 in children.

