### 9.2 Definition of Recommended Phase 2 Dose (RP2D)/ Tolerable Dose

The initial MTD defined in the adult trial is 112 mg/m^2/dose, approximated herein as dose

level 1 at 110 mg/m^2/dose. If there are < 2 DLTs in the first 6 patients treated at dose level 1 during the first cycle of therapy, this will be considered the RP2D and all subsequent patients will be enrolled at this dose level. If the MTD has been exceeded at Dose Level 1 as noted from the first six patients enrolled ( $\geq 2$  DLTs at least possibly attributed to IMG901), then the subsequent patients will be treated at Dose Level -1. If there are < 2 DLTs in the first 6 patients treated at dose level -1, this will be considered the RP2D and all subsequent patients will be enrolled at this dose level. A dose level -2 has been included in the proposal for purposes of providing a dose for those patients potentially accrued at dose level -1 (in the event it becomes the RP2D) and then subsequently requiring a dose reduction due to toxicity.

**Delayed Toxicity Monitoring:** We will monitor all serious adverse events on an ongoing basis. Analyses will be incorporated to screen for excess delayed peripheral neuropathy specifically.

A patient will be considered for toxicity monitoring if the patient is eligible and one of the following occurs: (1) completes one cycle of protocol therapy; (2) dies on protocol therapy for a reason considered possibly, probably, or likely related to protocol therapy; or (3) is removed from protocol therapy because of an adverse experience possibly, probably, or likely related to one of the agents. A toxicity-evaluable patient will be considered in the analysis during the interval from study enrollment until protocol therapy is terminated or, a toxicity-event is observed, whichever occurs first. A toxicity-evaluable patient will be considered to have experienced an excessive toxicity event if: (1) the patient dies on protocol therapy for a reason considered possibly, probably, or likely related to protocol therapy; or (2) experiences a dose-limiting toxicity.

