The analytic unit for monitoring for excessive toxicity will be the patient-cycle: Each cycle where an excessive toxicity event is observed or where the patient receives the agent and completes the full cycle of treatment will be considered in the analysis. If there is overwhelming evidence that the dose selected for this trial has a per-cycle-excessive peripheral neuropathy (Grade 3 or higher) probability of more than 1/3, such information will be presented to the DSMB and consideration will be given to modifying any defined RP2D to one dose level lower.

We will use a Bayesian rule to monitor for excessive peripheral neuropathy. We will assume a beta prior distribution with  $\alpha = 0.6$  and  $\beta = 1.2$ . At least once per month, we will calculate the posterior probability (given the data) that the probability of Grade 3 or higher peripheral neuropathy (“Excessive PN”) exceeds the 1/3 threshold:

$$P(p_{\text{Excessive PN}} > 1/3 | \text{Data}) = \int_{1/3}^1 \frac{\binom{n}{x} p^x (1-p)^{n-x} \frac{\Gamma(1.8)}{\Gamma(0.6)\Gamma(1.2)} p^{-0.4} (1-p)^{0.2}}{\int_0^1 \binom{n}{x} q^x (1-q)^{n-x} \frac{\Gamma(1.8)}{\Gamma(0.6)\Gamma(1.2)} q^{-0.4} (1-q)^{0.2} dq} dp$$

where n is the number of excessive-PN-evaluable cycles and x is the number of such cycles on which an excessive PN event is observed. If this posterior probability exceeds 80%, such information will be presented to the DSMB and consideration will be given to modifying any defined RP2D to one dose level lower. Examples of situations in which this rule will indicate excessive toxicity have been noted and are presented below:

Number of Excessive PN-Evaluable Cycles	Number of Cycles with Excessive PN Observed	$P(p_{\text{Excessive PN}} > 1/3 \mid \text{Data})$
5	3	0.848
10	5	0.834
15	7	0.837
20	9	0.843
25	11	0.852
30	13	0.860
35	15	0.869
40	17	0.876

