### 12.2 Data and Safety Monitoring Committee

To protect the interests of patients and the scientific integrity for all clinical trial research by the Children’s Oncology Group, the COG Data and Safety Monitoring Committee (DSMC) reviews reports of interim analyses of study toxicity and outcomes prepared by the study statistician, in conjunction with the study chair’s report. The DSMC may recommend the study be modified or terminated based on these analyses.

Toxicity monitoring is also the responsibility of the study committee and any unexpected frequency of serious events on the trial are to be brought to the attention of the DSMC. The study statistician is responsible for the monitoring of the interim results and is expected to request DSMC review of any protocol issues s/he feels require special review. Any COG member may bring specific study concerns to the attention of the DSMC.

The DSMC approves major study modifications proposed by the study committee prior to implementation (e.g., termination, dropping an arm based on toxicity results or other trials reported, increasing target sample size, etc.). The DSMC determines whether and to whom outcome results may be released prior to the release of study results at the time specified in the protocol document.

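### After six patients pass at a dose level, no numerical rule counts DLTs other than neuropathy: Section 9.2 defines an all-DLT event but attaches no threshold or action to it

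*Combined protocol and SAP*

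**What the plan says.** - **Entry check (Section 9.2).** "If there are < 2 DLTs in the first 6 patients treated at dose level 1 during the first cycle of therapy", then "this will be considered the RP2D and all subsequent patients will be enrolled at this dose level". The same rule is used at dose level -1, but only if dose level 1 fails.
- **Event definition (9.2, Delayed Toxicity Monitoring).** "A toxicity-evaluable patient will be considered to have experienced an excessive toxicity event if" the patient has a treatment-related death on therapy, or "experiences a dose-limiting toxicity". The patient-cycle is named as the unit for monitoring excessive toxicity.
- **The rule that follows (9.2).** "We will use a Bayesian rule to monitor for excessive peripheral neuropathy". The prior is Beta(0.6, 1.2), the limit is a per-cycle probability of 1/3 for Grade 3 or higher neuropathy, and the trigger is a posterior probability above 80%. It is calculated at least monthly. A flag goes to the DSMB, with consideration of a one-level lower RP2D. Both n and x are neuropathy counts.
- **Other oversight.** Section 9.2 promises ongoing monitoring of all serious adverse events. Section 12.2 has the DSMC review interim toxicity analyses and says that "any unexpected frequency of serious events on the trial are to be brought to the attention of the DSMC". Neither gives a count or a threshold.
- **Reporting.** Section 9.6 brings every dosed patient who has a toxicity or completes Cycle 1 into the toxicity evaluation. Section 9.4 tabulates toxicity by type and grade. Neither plans a DLT rate or an interval for one.
- **Context.** Tolerability is a primary aim (1.1.2), and Section 2.4 states: "There is no prior experience with IMGN901 in children".

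**The concern.** The event that 9.2 defines and the event that its rule counts are different. After the entry check, a run of renal, hepatic, haematological or meningitis-like DLTs would move no number in the plan, however long it became. These are plausible events: the single-agent adult DLTs in Section 2.3.1 include noninfective meningitis, headache, fatigue, renal failure and raised lipase as well as neuropathy.

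Six patients give a weak check, and most of the trial's patients are treated after it. A dose that passed by chance would be questioned on non-neuropathy toxicity only if someone judged the frequency unexpected. The data for a numerical check would already exist, because Section 11.12 collects every adverse event of Grade 3 or higher.

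**Working it through.** **1. The plan's own figures.** With x events in n cycles, the posterior is Beta(0.6 + x, 1.2 + n - x), and the reported quantity is its probability above 1/3. Recomputing the eight rows of the 9.2 table:

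| n / x | 5/3 | 10/5 | 15/7 | 20/9 | 25/11 | 30/13 | 35/15 | 40/17 |
|---|---|---|---|---|---|---|---|---|
| Stated | 0.848 | 0.834 | 0.837 | 0.843 | 0.852 | 0.860 | 0.869 | 0.876 |
| Recomputed | 0.8479 | 0.8343 | 0.8366 | 0.8434 | 0.8516 | 0.8601 | 0.8684 | 0.8765 |

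All agree to within 0.001, and each listed x is the smallest that exceeds 80%. The calculation used below is therefore the protocol's.

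**2. What the rule does not see (hypothetical data).** Take 40 cycles, 17 of them with a non-neuropathy DLT and none with Grade 3 neuropathy. The rule as written has x = 0, a posterior of about 1e-8, and no flag. Counting the 17 as events gives 0.876, above the trigger.

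**3. Strength of the six-patient check.** P(pass) = (1-p)^6 + 6p(1-p)^5.

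| True Cycle 1 DLT rate | 10% | 20% | 25% | 1/3 | 40% | 50% |
|---|---|---|---|---|---|---|
| P(0 or 1 DLT in 6) | 0.886 | 0.655 | 0.534 | 0.351 | 0.233 | 0.109 |

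The Clopper-Pearson 95% upper limit after 1 DLT in 6 is 64%.

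**4. What a second run of the same calculation would add.** The documents give no limit for DLTs of any type. Assume the same prior, a limit of 1/3 per patient for Cycle 1 DLTs, and the same 80% cut-off. Condition on 0 or 1 DLT in the first six, and compute exactly the chance of a flag at any later look.

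Inputs:
- Primary strata: 3 × 19 = 57 enrolled at most (9.1.1).
- All six strata: 6 × 19 = 114.
- Accrual in the primary strata: 18 + 14 + 9 = 41 a year, or 41/12 = 3.4 a month. A monthly look is therefore one every 3 to 4 patients.

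In each range below, one end is a look every 3 to 4 patients (first look at patient 9 or 10) and the other is a look after every patient from the seventh.

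| True rate | Flag by 57 | Flag by 114 |
|---|---|---|
| 15% | 0.1% | 0.1% |
| 20% | 0.5-0.9% | 0.5-0.9% |
| 25% | 3-4% | 3-4% |
| 1/3 | 20-24% | 31-34% |
| 40% | 52-57% | 77-80% |
| 50% | 92-93% | over 99% |

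**5. Both steps together, by 57 patients.** The chance that a dose passes at six and is still unflagged is P(pass) × (1 - flag):
- 1/3: 0.351 × (0.76 to 0.80) = 27-28%
- 40%: 0.233 × (0.43 to 0.48) = 10-11%
- 50%: 0.109 × (0.07 to 0.08) = under 1%

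**The case against.** The best case against is that the neuropathy focus is deliberate. Section 9.2 says the delayed analyses target neuropathy specifically. The background supports that: it was the most frequent treatment-related event among 198 single-agent adults, and 36% had Grade 3 neuropathy at 112 mg/m² in the combination study. The starting dose comes from adult experience, each DLT leads to patient-level modification under Section 5, and the DSMC may recommend modification or termination. On this view an all-DLT boundary is a preference. That explains why neuropathy has a rule. It does not explain why 9.2 defines a wider event, gives it a unit, and never uses it.

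Three stronger readings are tempting, and the documents do not support them:
- *A dose that passes is never formally tested again.* It is tested at least monthly for Grade 3 or higher neuropathy, and a flag can lead to a lower RP2D. The gap concerns other DLTs and related deaths.
- *The tolerability conclusion uses 6 of 114 patients.* Sections 9.4 and 9.6 tabulate toxicity in all evaluable patients. Only the decision that fixes the RP2D rests on six.
- *Other toxicity is unmonitored.* Serious-event monitoring, expedited reporting and DSMC review all exist, but without a number. They are also not a full substitute: Section 11.10 exempts Grade 1-4 myelosuppression from expedited reporting, while Section 5.2.2 makes Grade 4 neutropenia lasting more than 7 days a DLT.

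Two limits on the remedy stand. At a true rate of exactly 1/3 it misses more often than it detects. The 114-patient figures are a ceiling: Section 9.1.1 ends enrolment when the primary strata finish unless the secondary strata are extended, and 10 + 8 + 5 = 23 primary-stratum patients had enrolled before Amendment #1.

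**Conclusion.** The point holds as a gap between definition and rule. Section 9.2 defines an all-DLT event and leaves it without a threshold or action. Beyond the six-patient check, non-neuropathy DLTs and related deaths depend on judgement alone. That check lets through a dose with a 33%, 40% or 50% Cycle 1 DLT rate 35%, 23% or 11% of the time.

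The pass probabilities follow from the plan alone. The detection figures rest on assumptions: a per-patient limit of 1/3, borrowed from the per-cycle neuropathy rule; an 80% cut-off; Cycle 1 DLTs only; one common DLT rate across strata and ages; and the look schedules shown. Under them, a second run cuts the chance that a 40% dose passes and stays unflagged from 23% to 10-11% by 57 patients. At 50% the chance falls from 11% to under 1%. The run detects clearly excessive rates, not borderline ones. The change is worthwhile and cheap, and the trial does not fail without it.

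**What to change.** In Section 9.2, Delayed Toxicity Monitoring:
1. Run the existing posterior calculation a second time at the same monthly look. Let n be all toxicity-evaluable patients at the current dose level, pooled over strata and including those already treated. Let x be those with a DLT or treatment-related death. If the posterior exceeds the cut-off, refer to the DSMC (9.2 says DSMB and 12.2 says DSMC; use one name). The flag is a referral only and sets no dose.
2. State the per-patient 1/3 limit and the 80% cut-off as assumptions for the sponsor to confirm, and show the table in step 4 of the working as the operating characteristics.
3. Say whether DLTs after Cycle 1 count. The event in 9.2 runs over all cycles. A Cycle 1 count per patient leaves later non-neuropathy DLTs outside the rule. If they are to count, the unit, the limit and the operating characteristics must be reset.
4. If the sponsor prefers six patients plus DSMC judgement, say so and remove the unused event definition.

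In Section 9.4, report the Cycle 1 DLT rate over all evaluable patients at the dose used, with a Clopper-Pearson interval, as the answer to aim 1.1.2.

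Cost: one paragraph, one extra line in a monthly calculation and one extra estimate. No new data or patients are needed. The price is a false referral in 0.1% of trials at a true rate of 15%, under 1% at 20% and 3-4% at 25%, given that the dose passed at six.

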### 9.3 Study Design

This trial is a multi-strata Phase 2 study of IMG901. The primary endpoint will be objective response by RECIST criteria. As of Amendment #1, each stratum will accrue a maximum of 16 evaluable patients. IMG901 will be identified as having sufficient activity for further study in a particular stratum if there are at least 4 responses (PR or CR) confirmed by central review. This design will be used for all strata which have not been closed prior to the activation of Amendment #1.

We will consider the agent not of sufficient interest for further evaluation in a disease category if the true response rate is 15%. ( $H_0$  is a true response rate of 15%.)  $H_a$  is a true response rate of 40%. Each stratum will accrue 16 evaluable patients. Thus, there will be a maximum of 96 evaluable patients. If the agent has a true response rate of 15%, the rule described herein will identify the agent of sufficient activity for further study with probability 0.079 (Type I error). If the agent has a true response rate of 40%, the rule described herein will identify the agent of sufficient activity for further study with probability 0.833 (power against the alternative hypothesis  $p = 0.40$ ). In addition to making the decision to accept or reject the drug, the final results will be reported after all patients have been identified as having a CR, PR, or PD as their response according to protocol-specified criteria.

Prior to Amendment #1, the trial used a Simon two-stage optimal design in each stratum. The best response of disease was examined separately in each stratum. Within each stratum, the following two-stage design for 15% response rate vs. 40% response rate with  $\alpha = \beta = 0.10$  was employed:

	Cumulative Number of Responses at the End of the Stage	Decision
Stage 1: Enter 10 evaluable patients	0 or 1 2 or more	Terminate the trial for this stratum because the agent is ineffective. Proceed to Stage 2.
Stage 2: Enter 12 additional evaluable patients	5 or fewer 6 or more	Terminate the trial for this stratum because the agent is ineffective. Terminate the trial for this stratum because the agent is effective.

A comparison of the operating characteristics of the single stage and two-stage designs

appears below.

True response rate	Simon's optimal design (10 + 12 [2,6])			Single- stage design (16[4])
	Probability of stopping early for lack of activity	Probability of identifying agent as effective	Expected number of patients accrued	Probability of identifying agent as effective
5%	0.914	0.001	11.03	0.001
10%	0.736	0.016	13.17	0.017
15%	0.544	0.091	15.47	0.079
20%	0.376	0.246	17.49	0.202
25%	0.244	0.451	19.07	0.370
30%	0.149	0.650	20.21	0.550
35%	0.086	0.804	20.97	0.711
40%	0.046	0.903	21.44	0.833
45%	0.023	0.957	21.72	0.915
50%	0.011	0.983	21.87	0.962

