#### 3.2.3 Disease Status

- 3.2.3.1 Patients must have radiographically measurable disease (with the exception of those with neuroblastoma, see [Section 3.2.3.2](#)).

Measurable disease is defined as the presence of at least one lesion on MRI or CT scan that can be accurately measured with the longest diameter a minimum of 10 mm in at least one dimension (CT scan slice thickness no greater than 5 mm).

Note: The following do not qualify as measurable disease:

- malignant fluid collections (e.g., ascites, pleural effusions)
- bone marrow infiltration except that detected by MIBG scan for neuroblastoma, see [Section 3.2.3.2](#)
- lesions only detected by nuclear medicine studies (e.g., bone, gallium or PET scans) except as noted in [Section 3.2.3.2](#)
- elevated tumor markers in plasma or CSF
- previously radiated lesions that have not demonstrated clear progression post radiation
- leptomeningeal lesions that do not meet the measurements noted above.

3.2.3.2 Patients with **neuroblastoma** who do not have measurable disease but have MIBG-avid evaluable disease are eligible.

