#### 4.1.3 Criteria for Starting Subsequent Cycles

A cycle may be repeated every 21 days if the patient has at least stable disease, has again met laboratory parameters as defined in the eligibility section ([Section 3.2.5](#)) and has not met one of the Off Protocol Therapy or Off Study Criteria ([Section 8.0](#)). Patients who have experienced dose-limiting toxicity (DLT) (see

[Section 5.0](#)) in the previous cycle should have the dose modified (see [Section 4.1.4](#)). Treatment may consist of up to 17 cycles, for a total duration of therapy approximating 12 months, absent disease progression or unacceptable toxicity. To continue on therapy the patient must have at least clinically and radiographically stable disease. Radiographic disease evaluations will be done after the 2nd cycle of therapy, after every other cycle until 6 months, and then every 3 months.

4.1.4 Dose Schema:

The starting dose will be 110 mg/m^2 (dose level 1). For patients with toxicities as outlined in [Section 5.0](#) and who recover to starting criteria within 7 days as outlined in [Section 4.1.3](#), a single dose reduction to the next lowest dose level will be allowed.

Dose Level	IMGN901 (mg/m  )	Day(s) of Administration
-2	75	1 and 8
-1	90	1 and 8
1*	110	1 and 8

\*Starting dose level

Further dose reduction for toxicity will be considered if dose level -1 is not tolerated. No dose escalations will occur.

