#### 9.4 Methods of Analysis

Response criteria are described in [Section 10.0](#). A responder is defined as a patient who achieves a best response (as defined in [Section 10.6](#)) of PR or CR on the study. Response rates will be calculated as the percent of evaluable patients who are responders, and Clopper-Pearson confidence intervals will be constructed.

Toxicity tables will be constructed to summarize the observed incidence by type of toxicity and grade. A patient will be counted only once per cycle for a given toxicity for the worst grade of that toxicity reported for that patient. Toxicity information recorded will include the type, severity, time of onset, time of resolution, and the probable association with the study regimen.

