#### 9.5 Evaluability for Response

Any eligible patient who receives at least one dose of IMG901 will be considered evaluable for response with the following exception: if a patient receives non-protocol anti-cancer therapy (including surgery) during the response evaluation period after the patient is considered as having a partial or complete response but prior to confirmation of this status by tumor imaging and before progressive disease is noted, the individual will be considered inevaluable for the response endpoint. Further, patients who stop IMG901 after the first evaluation because of toxicities or death will be considered evaluable for the response evaluation and will be counted as non-responders for the response endpoint. Patients who demonstrate a complete or partial response confirmed by central review will be considered to have experienced a response for the application of the rule given in [Section 9.2](#). The evaluation period for determination of the best response will be 6 treatment cycles. All other patients will be considered non-responders. All patients considered to have a response (CR or PR) must have imaging studies reviewed centrally at the COG. Centers will be notified by the COG about requests for scans of patients with stable disease. See [Section 7.3](#) regarding shipping instructions. Preliminary assessment of activity using institutionally provided tumor measurements will be entered into CDUS quarterly. The central review by COG will be provided as the final reviewed assessment of response when such becomes available.

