### 10.2 Response Criteria

As outlined, patients will be assigned to one of the following categories for assessment of response: a) solid tumor and measurable disease ([Section 10.3](#)); b) neuroblastoma with MIBG positive lesions ([Section 10.4](#)); c) neuroblastoma with bone marrow involvement ([Section 10.5](#)); Note: Neuroblastoma patients who do not have MIBG positive lesions or bone marrow involvement should be assessed for response as solid tumor patients with measurable or evaluable disease.

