10.3.4 Overall Best Response Assessment

Each patient will be classified according to their “best response” for the purposes of analysis of treatment effect. Best response is determined from the sequence of the objective statuses described in [Section 10.6 \(Tables 1-3\)](#).

10.4 **Response Criteria for Neuroblastoma Patients with I-MIBG Positive Lesions**10.4.1 MIBG Positive Lesions

Patients who have a positive MIBG scan at the start of therapy will be evaluable for MIBG response. The use of I for MIBG imaging is recommended for all scans. If this isotope is unavailable at the treating institution, the use of the same radioisotope for all MIBG scans for an individual patient is strongly encouraged.

10.4.2 The following criteria will be used to report MIBG response by the treating institution:

- **Complete Response:** Complete resolution of all MIBG positive lesions
- **Partial Response:** Resolution of at least one MIBG positive lesion, with persistence of other MIBG positive lesions.
- **Stable Disease:** No change in MIBG scan in number of positive lesions (includes patients who have same number of positive lesions but decreased density).
- **Progressive Disease:** Development of new MIBG positive lesions.

[figure not shown]
10.4.3 The response of MIBG lesions will be assessed on central review using the Curie scale as outlined below. Central review responses will be used to assess efficacy for study endpoint. See [Section 7.3](#) for details on transferring images to the Imaging Research Center.

NOTE: This scoring is NOT required to be done by the treating institution for end of course response assessments.

The body is divided into 9 anatomic sectors for osteomedullary lesions, with a 10th general sector allocated for any extra-osseous lesion visible on MIBG scan. In each region, the lesions are scored as follows. The **absolute extension score** is graded as:

- 0 = no site per segment,
- 1 = 1 site per segment,
- 2 = more than one site per segment,
- 3 = massive involvement (>50% of the segment).

The **absolute score** is obtained by adding the score of all the segments. See diagram of sectors below:

The **relative score** is calculated by dividing the absolute score at each time point by the corresponding pre-treatment absolute score. The relative score of each patient is calculated at each response assessment compared to baseline and classified as below:

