1. **Complete response:** all areas of uptake on MIBG scan completely resolved. If morphological evidence of tumor cells in bone marrow biopsy or aspiration is present at enrollment, no tumor cells can be detected by routine morphology on two subsequent bilateral bone marrow aspirates and biopsies done at least 3 weeks apart to be considered a **Complete Response**.
2. **Partial response:** Relative score  $\leq 0.2$  (lesions almost disappeared) to  $\leq 0.5$  (lesions strongly reduced).
3. **Stable disease:** Relative score  $> 0.5$  (lesions weakly but significantly reduced) to 1.0 (lesions not reduced).
4. **Progressive disease:** New lesions on MIBG scan

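### Neuroblastoma stratum: the RECIST sentence in 9.3 and the CT/MRI opening of 10.6 were not adapted to the MIBG response the plan counts, and Table 3 leaves MIBG PR with a cleared bone scan without a category

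*Combined protocol and SAP*

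**What the plan says.** Section 9.3 sets one endpoint for all strata: "The primary endpoint will be objective response by RECIST criteria". A stratum is positive with at least 4 centrally confirmed responses among 16 evaluable patients. The same section later says results are reported under the protocol's own criteria.

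Section 3.2.3.2 makes an exception to measurable disease: neuroblastoma patients "who do not have measurable disease but have MIBG-avid evaluable disease are eligible". Section 10.2 gives "neuroblastoma with MIBG positive lesions" its own response category, scored under 10.4. Section 10.4.3 describes the central Curie score and says "Central review responses will be used to assess efficacy for study endpoint".

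Section 9.4 reads "A responder is defined as a patient who achieves a best response" of PR or CR as defined in 10.6. Section 10.6, headed for solid tumors, opens with two determinations by CT or MRI at least 3 weeks apart. Its later sentences also require two determinations but name no modality. Its Table 1 gives sequences over time. Tables 2 and 3 combine CT/MRI, MIBG, bone scan, marrow and catecholamines into an overall status. Section 10.4.4 refers to a sequence in Table 3, which holds none.

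In Table 3 the SD row and both PR rows carry the bone scan entry *Non-CR, Non-PD*, which 10.4.5 defines as neither CR nor PD. Table 2 has *Non-PD* in that column for its SD and PR rows. Bone scans are optional (10.4.5), and marrow histology is required only with a history of involvement (10.5.1).

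Section 9.5 first counts as responders those with a centrally confirmed CR or PR, then adds "All other patients will be considered non-responders".

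**The concern.** Stratum 3 is one of three primary strata, and its decision turns on a handful of responses in 16 patients. Two things are then unsafe.

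First, the sentence that names the endpoint, read alone, does not describe the response that Section 10 counts for patients without a RECIST-measurable lesion. Nor does the plan expressly say whether an MIBG-only response needs a second determination on MIBG.

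Second, Table 3 breaks its own ordering. Clearing the bone scan moves a patient with MIBG PR from a listed PR to no listed category. A dispute about such a patient would arise after the response is known, when the choice can no longer be made blind to its effect on the count.

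**Working it through.** The plan gives no figure on this point to reproduce. The check is a comparison of texts and an enumeration of the two tables.

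**Endpoint wording.** For an MIBG-only patient:

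- 9.3: RECIST response. No target lesion, so PR cannot be reached.
- 9.4 with 10.6, Table 3: MIBG PR or CR yields overall PR or CR.
- 10.4.3: central MIBG review decides the endpoint.
- 10.6, opening: CT or MRI determinations. Later sentences: two determinations, modality open.

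Three places count MIBG response. Two sentences do not fit them.

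**Enumeration.** Non-progressing states only. CT, MIBG: CR, PR, SD. Bone scan: CR or neither CR nor PD. Marrow: CR or SD. Catecholamines: elevated or normal. *Non-PD* is taken as any non-progressing result.

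Table 2: 3 × 3 × 2 × 2 × 2 = 72 states. Listed:
- CT SD with any MIBG: 3 × 8 = 24
- CT PR with MIBG CR or PR: 2 × 8 = 16
- CT CR with MIBG PR: 8
- CT CR, MIBG CR, elevated catecholamines: 4
- full CR row: 1

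Total 53, so 72 − 53 = 19 are unlisted: 16 are CT CR or PR with MIBG SD (2 × 8), and 3 are CT CR with MIBG CR.

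Table 3 (no new lesion): 3 × 2 × 2 × 2 = 24 states. Listed:
- MIBG SD, bone scan neither CR nor PD: 4
- MIBG PR, same bone scan: 4
- MIBG CR, same bone scan, elevated catecholamines: 2
- full CR row: 1

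Total 11, so 24 − 11 = 13 are unlisted: MIBG SD with bone scan CR 4, MIBG PR with bone scan CR 4, MIBG CR 5. Of the 12 states with bone scan CR, only the CR row is listed.

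**Unlisted states with MIBG CR or PR:** 3 + 9 = 12. Some are ruled out if the component definitions are applied inside the tables:

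| Reading | Table 2 | Table 3 | Total |
|---|---|---|---|
| As printed | 3 | 9 | 12 |
| Drop MIBG CR with marrow not CR (10.4.3) | 1 | 6 | 7 |
| Also drop marrow CR with elevated catecholamines (10.5.1) | 1 | 4 | 5 |

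The 10.4.3 clause requires, where marrow was positive at enrollment, that "no tumor cells can be detected by routine morphology on two subsequent bilateral bone marrow aspirates and biopsies" before MIBG CR is given. The 10.5.1 clause requires catecholamines raised at enrollment to normalize before marrow CR is given.

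The last 5 are MIBG PR with bone scan CR in Table 3 (3 states), and MIBG CR, bone scan neither CR nor PD, marrow CR, normal catecholamines (1 in each table, with CT CR in Table 2). All 5 need a bone scan result. Had Table 3 used *Non-PD* in its SD and PR rows, the totals would be 6 as printed and 2 after both clauses.

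**How MIBG PR with bone scan CR would be counted.** The first part of 9.5 with 10.4.3: a relative score of at most 0.5 on central review is a partial response and counts, so responder. Table 3 with the closing residual of 9.5: no row, so non-responder.

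**The case against.** The strongest reply is that this is copy-editing. Section 9.4 directly follows 9.3 and gives the operative responder definition through Section 10. Section 9.3 itself defers to the protocol's criteria for reporting. The confirmation sentences in 10.6 that fix a best response of CR or PR name no modality. Bone scan criteria apply only if scans were done at baseline and later, and marrow is used as a component of overall response, so the columns are already conditional. The main gap needs an MIBG-only patient, an optional positive baseline scan, a repeat, full clearing on it, and only partial MIBG clearing.

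Most of this stands as a limit on severity. It does not remove the contradiction between 9.3 and 10.4.3, and it leaves Table 3 ranking a better state below a worse one. The CR rows still ask for CR in columns that may never have been assessed.

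The counts also depend on how far the component clauses carry into the tables. Section 10.3.3 makes catecholamine normalization part of CR, yet Table 2 lists CT CR with elevated catecholamines. That suggests the clauses are not applied column by column, in which case 12 is the figure. Applying both clauses gives 5; applying only the marrow clause gives 7, which fits neither consistent reading.

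**Conclusion.** The point holds as two unadapted sentences and a table error that should be corrected. As printed, 12 non-progressing states with MIBG CR or PR have no category; 5 remain if both component clauses are applied. These are counts of states, not of patients. The effect on the stratum decision cannot be sized: the documents give no MIBG-only share, no bone scan frequency and no frequency of these states.

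Three stronger readings are tempting, and the documents do not support them.

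- A reader might infer that stratum 3 has no endpoint for MIBG-only patients, or that they sit in the denominator without being able to respond, at a cost in power. Sections 9.4, 10.2, 10.4.3 and Table 3 show that their response is meant to count.
- A reader might infer that MIBG PR with a cleared bone scan is plainly a non-responder. That is one of two readings; 10.4.3 with the first part of 9.5 gives the opposite.
- A reader might infer that CT CR or PR with MIBG SD must be SD, because in all 53 listed Table 2 states the overall status is no better than the worse of CT and MIBG. That is extrapolation to a pattern the table leaves out, and it would overrule a RECIST response that 9.3 names. The sponsor has to decide it.

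**What to change.** 1. In 9.3, define the stratum 3 endpoint as centrally reviewed overall best response under Tables 2 and 3 (10.3 for patients whom 10.2 sends there), and RECIST 1.1 response for the other strata.
2. In 10.6, state that the rule of two determinations at least 3 weeks apart applies to MIBG for MIBG-only patients. Make 10.4.4 cite Table 1 for the sequence and Table 3 for each status.
3. In Table 3, change the bone scan entry to *Non-PD* in the SD row and both PR rows. In both tables, rate MIBG CR (with CT CR, or no new lesion) and no PD as PR whenever the full CR row is not met. All 24 Table 3 states then have a category, as do 56 of 72 in Table 2 (72 − 16), and no listed state changes.
4. Allow not done or not applicable for bone scan and not involved for marrow, including in the CR rows.
5. Have the sponsor specify the category for CT CR or PR with MIBG SD (the remaining 16 states) before stratum 3 results are reviewed, and report the RECIST-only rate for patients with measurable disease alongside.

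The cost is protocol wording and table edits; sample size and threshold do not change. Section 7.3 already sends responders' MIBG scans for central review. Under 4.1.3, imaging follows cycle 2 and then "after every other cycle until 6 months, and then every 3 months", so assessments are 2 × 21 = 42 days apart and fall after cycles 2, 4 and 6 of the 6-cycle response window in 9.5. The 3-week rule needs no extra scan if MIBG follows that schedule. That is an assumption, because the detailed observation schedule is not in the text available.
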